4.1.1.1. Phase 1b Overview

This is a multicenter, open-label, nonrandomized, phase 1b, dose-finding study of TRC105 in combination with standard dose axitinib in patients with advanced RCC. Escalating doses of i.v. TRC105 will be administered weekly beginning with Dose Level 1 in combination with oral axitinib given as 5 mg p.o. BID daily. Intermediate dose TRC105 (below the MTD established during the trial) may be explored based upon clinical, PK, and/or biomarker data.

Weekly Dosing:

Dosing will begin at 8 mg/kg (cohort 1) however a -1 cohort has also been included (6 mg/kg) and will be enrolled if 8 mg/kg TRC105 plus axitinib exceeds the MTD. The first weekly TRC105 dose will be split into two doses whereby 3 mg/kg is administered on cycle 1 day 1 and the balance is administered on cycle 1 day 4. The entire weekly dose of TRC105 (6, 8 or 10 mg/kg) is then given on cycle 1 day 8 and weekly thereafter in combination with oral axitinib given as 5 mg p.o. BID. Those who tolerate TRC105 without any infusion reactions may be eligible for reduced infusion durations and decreased premedication (see [Section 6.1.6](#)).

Every Two Week Dosing:

In cohort 3 (10 mg/kg weekly during cycle 1; 15 mg/kg every two weeks beginning with cycle 2 day 1) and cohort 4 (10 mg/kg weekly during cycle 1; 20 mg/kg every two weeks beginning with cycle 2 day 1) the first weekly TRC105 dose will also be split into two doses whereby 3 mg/kg is administered on cycle 1 day 1 and the balance is administered on cycle 1 day 4. Starting on cycle 2 day 1 and beyond, TRC105 will be administered every two weeks on days 1 and 15.

After 2 cycles of treatment, patients who demonstrate a response of complete response (CR), partial response (PR) or stable disease (SD) will be eligible for additional treatment until progression.

Patients who exit the study for reasons other than drug-related dose-limiting toxicity prior to completion of the first 28-day cycle will be replaced. Inpatient dose escalation of TRC105 is not allowed.

Table 5: Dose Levels

Cohort	Number of Evaluable Subjects	Axitinib mg p.o., BID days 1-28	TRC105 mg/kg IV
-1	3-6	5	6 ^a

Cohort	Number of Evaluable Subjects	Axitinib mg p.o., BID days 1-28	TRC105 mg/kg IV
1 (Starting Dose)	3-6	5	8 ^a
2	3-6	5	10 ^a
Expanded Cohort 1	9-12 (up to 15 total at the MTD)	5	10 ^a
3	3-6	5	
 • 10 mg/kg weekly during cycle 1^b • 15 mg/kg every two weeks beginning with cycle 2 day 1^b

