4	3-6	5	
 • 10 mg/kg weekly during cycle 1^b • 20 mg/kg every two weeks beginning with cycle 2 day 1^b
Expanded Cohort 2	At least 6 patients will be treated at the MTD (either cohort 3 or cohort 4 dose level)	5	
 • 10 mg/kg weekly during cycle 1^b • Either 15 or 20 mg/kg every two weeks beginning cycle 2 day 1^b

^a In cohort -1, 1, 2 and Expanded Cohort 1 TRC105 will be given weekly.

^b In cohorts 3 and 4 and Expanded Cohort 2, axitinib dosing will begin on cycle 1 day 1 and twice daily thereafter, and TRC105 will be administered weekly during cycle 1. The first weekly TRC105 dose will be split into two doses whereby 3 mg/kg is administered on cycle 1 day 1 and the balance is administered on cycle 1 day 4. Starting on cycle 2 day 1 and beyond, TRC105 will be administered every two weeks on days 1 and 15.

For cohorts 1 and 2, the DLT evaluation period, for purposes of dose expansion, will be the first 28 days of dosing axitinib and TRC105 together (e.g., from cycle 1 day 1 through cycle 1 day 28). Cycles are 28 days in duration.

For cohorts 3 and 4, the DLT evaluation will be the first 28 days of dosing axitinib with TRC105 every 2 weeks (e.g., from cycle 2 day 1 through cycle 2 day 28). Cycles are 28 days in duration.

Three patients will be initially enrolled and treated at each dose level. If none of these 3 patients experiences a dose-limiting toxicity (DLT) during the 28-day evaluation period, dose escalation will proceed following review of safety data with appropriate site staff including the principal investigators at all sites.

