10. **Urinalysis:** To be performed locally. Microscopic analysis and/or urine protein creatinine ratio or 24-hour urine protein collection should be performed as clinically indicated.
11. **TRC105 Administration:** Intravenous TRC105 is diluted in normal saline. TRC105 will be administered weekly during cycle 1. The first weekly TRC105 dose will be split into two doses whereby 3 mg/kg is administered on cycle 1 day 1 and the balance is administered on cycle 1 day 4. Starting on cycle 2 day 1 and beyond, TRC105 will be administered every two weeks on days 1 and 15. See [Section 6.1.6](#) for specific TRC105 administration guidelines.
12. **Axitinib Dosing:** Oral axitinib will be dosed twice daily on days 1-28 of each 28 day cycle according to the axitinib package insert. Patients who tolerate the starting dose with no adverse reactions above grade 2 for four weeks will have the axitinib dose increased. See [Section 6.2](#) for specific dosing guidelines.
13. **Imaging:** CT or MRI Images of the chest, abdomen, and pelvis to be performed at screening, and on-study as outlined in the assessment table. In addition, a brain MRI or CT with contrast to be performed at screening to assure absence of CNS metastases and on study as needed if metastases are suspected. Bone scans are to be performed at screening and throughout the study at the time of CT assessments if bone metastases are present

and cannot be followed by CT. Known areas of disease should be consistently followed throughout the study. Assessments should be performed whenever disease progression is suspected. Allowable window for tumor imaging studies is +/- 7 days. Scans will be every 56 days from cycle 1 day 1.

14. **12-Lead ECG:** Single tracing 12-lead ECG will be performed at screening and at time points indicated in the Schedule of Assessments (pre-dose). For a QTc > 500 ms, a repeat ECG for confirmation and evaluation of the ECG by a cardiologist is recommended. Additional ECGs may be performed on study as clinically indicated.
15. **Concomitant Medications and Treatments:** Concomitant medications and treatments will be recorded from 28 days prior to the start of study treatment and up to 28 days following the last dose of study treatment. Required TRC105 premedications should be recorded on TRC105 premedications CRF.

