6.2.6. Axitinib Dose Modification

Patients who are intolerant of axitinib may continue TRC105 treatment alone on the study.

Axitinib should be held for two weeks prior and for two weeks following surgical procedures.

Dose reduction is allowed based on individual safety and tolerability. Following dose interruption, axitinib treatment may be reinitiated when the toxicity that prompted dose reduction has resolved to baseline or grade 1. See axitinib package insert in [Section 20.3](#).

All patients will initially receive axitinib 5 mg twice daily; patients randomized to receive TRC105 will receive TRC105 at 3 mg/kg on day 1, 7 mg/kg on day 4, and 10 mg/kg on day 8 and weekly thereafter. Patients **in both arms** who tolerate axitinib for at least two consecutive weeks with no adverse reactions > Grade 1 considered clinically significant (according to the Common Toxicity Criteria for Adverse Events [CTCAE]), will, at the discretion of their treating physician, have the axitinib dose increased to 7 mg twice daily beginning on cycle 2 day 1, unless the patient's blood pressure is > 150/90 or the patient is receiving more than one antihypertensive medication. Subsequently, with the same criteria, patients who tolerate the axitinib dose of 7 mg twice daily for at least two consecutive weeks may have the axitinib dose increased to a maximum of 10 mg twice daily beginning with cycle 3 day 1. Dose reductions of axitinib and TRC105 are allowed per patient tolerance (including to doses of axitinib between 5 and 10 mg twice daily). Reasons for dose reduction and reasons for not increasing the axitinib dose will be documented on the CRF.

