Patients assigned to the combination arm who cannot tolerate axitinib therapy and who demonstrate a response of complete response (CR), partial response (PR) or stable disease (SD) with the combination and are thought to benefit from continued TRC105 therapy may continue on study on TRC105 alone.

Table 17: Ideal Axitinib Dose Escalation Schedule

Axitinib Available Dose Levels	Cycle Day
5 mg BID	Cycle 1 Day 1 to Cycle 2 Day 1
7 mg BID	Cycle 2 Day 1 to Cycle 3 Day 1
10 mg BID	Cycle 3 Day 1+

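### The axitinib footnote in all five assessment schedules gives a different, mostly looser rule for raising the dose than Section 6.2.6

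*Protocol*

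**What the plan says.** The same sentence stands in Table 7 footnote 12, Table 8 footnote 12, Table 9 footnote 11, Table 10 footnote 12 and Table 11 footnote 12: "Patients who tolerate the starting dose with no adverse reactions above grade 2 for four weeks will have the axitinib dose increased". Each of these footnotes begins by referring to the axitinib package insert and ends by pointing to Section 6.2.

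Protocol Section 6.2.6 gives the detailed rule. It requires "at least two consecutive weeks with no adverse reactions > Grade 1 considered clinically significant" and leaves the increase to the treating physician. It blocks the increase if blood pressure is above 150/90 "or the patient is receiving more than one antihypertensive medication". The first step is to 7 mg twice daily from cycle 2 day 1. Table 17 places that dose at "Cycle 2 Day 1 to Cycle 3 Day 1" and carries no phase or cohort limit. The section also provides that "reasons for not increasing the axitinib dose will be documented on the CRF". The Synopsis and Section 4.1.1.2 state the same rule under Phase 2.

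For Phase 1b, Table 5 (Section 4.1.1.1) has a column headed "Axitinib mg p.o., BID days 1-28" with 5 in every row. Section 6.2.2 makes clear that 5 mg is the initial dose. For cohorts 3 and 4 the DLT window is the first 28 days of dosing "every 2 weeks (e.g., from cycle 2 day 1 through cycle 2 day 28". The only bar on raising a dose within a patient in that section is "Inpatient dose escalation of TRC105 is not allowed".

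**The concern.** The protocol states one operational rule in two ways. A site working from the schedule of assessments would raise axitinib in some patients whom the detailed section excludes. The footnote says they *will* be raised, whereas Section 6.2.6 leaves the decision to the physician. No text says in so many words which criterion governs.

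What is at stake is mainly patient safety and consistent dosing across sites. The Section 6.2.6 conditions keep a higher dose away from patients who already have a clinically significant reaction or whose blood pressure takes more than one drug to control. Grade 1 to 3 hypertension was seen earlier in Phase 1b (Section 2.3.4.1). In cohorts 3 and 4 the increase would also fall at the start of the DLT window. Hypertension is not among the exceptions to the grade 3 or 4 nonhematologic DLT rule in Table 6.

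**Working it through.** The plan gives no figure for titration, so the check is mainly a comparison of texts.

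**1. The two rules side by side**

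| Element | Schedule footnote (Tables 7 to 11) | Section 6.2.6 |
|---|---|---|
| Grade that blocks the increase | above 2 | above 1, if clinically significant |
| Period to be clear | four weeks | two consecutive weeks or more |
| Physician discretion | none stated | yes |
| Blood pressure | none stated | not above 150/90 |
| Antihypertensives | none stated | at most one |
| Target dose | none stated | 7 mg, then up to 10 mg, twice daily |
| Patients addressed | each schedule's own patients | randomized patients, both arms |

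The footnote is looser on everything except duration.

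**2. Patients on whom the rules disagree**

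- *Clinically significant grade 2 reaction that leaves no clear two-week run before cycle 2 day 1.* Nothing is above grade 2, so the footnote raises the dose. Section 6.2.6 does not.
- *Two antihypertensives at entry, pressure controlled, hypertension unchanged.* Exclusion criterion 8 (Section 5.1.2) limits blood pressure but not the number of drugs, so such a patient can enrol. Section 10.5 counts a pre-existing condition as a treatment-emergent event if it worsens. Unchanged hypertension is therefore not a reaction above grade 2, and the footnote raises the dose. Section 6.2.6 does not.
- *Hypertension that arises or worsens on study.* The answer depends on its CTCAE grade. Appendix 1 only links to CTCAE, so the documents cannot settle this case.

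**3. Timing.** Four weeks from cycle 1 day 1 ends on cycle 1 day 28, so the footnote's increase falls on cycle 2 day 1. Section 6.2.6 and Table 17 give the same day. In cohorts 1 and 2 the DLT window closes on cycle 1 day 28, before the increase. In cohorts 3 and 4 it opens on cycle 2 day 1. The 10 mg step comes at cycle 3 day 1, after that window.

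**4. Size of the step**

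- 5 mg × 2 × 28 = 280 mg per cycle
- 7 mg × 2 × 28 = 392 mg per cycle
- 392 / 280 = 1.40, or +40%

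**5. What one DLT changes in cohorts 3 and 4** (Section 4.1.1.1; SAP Section 3.1)

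- Each cohort has 3 to 6 evaluable patients, so the two together have 6 to 12.
- 0/3 becoming 1/3 expands the level to six.
- 1/6 = 16.7% does not exceed the MTD. 2/6 = 33.3% does.

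The documents give neither the number of patients raised under the footnote against Section 6.2.6 (anything from 0 to 6 per level) nor the effect of 7 mg on the DLT rate. No change in the DLT rate is therefore computed.

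**The case against.** The strongest reply is that the footnote is only a summary. It refers to the package insert and to Section 6.2 for the specific guidelines. It names no target dose, so a site cannot carry out an increase from it alone. Three places in the protocol state the detailed rule consistently. Section 6.2.6 also tells sites to reduce axitinib for persistent hypertension despite medication. All of this lowers the chance of error. It does not remove it, because the footnote states its own complete criterion, with *will*, before pointing elsewhere.

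A second reply is that the Section 6.2.6 paragraph speaks of randomized patients and both arms, so it may not govern Phase 1b at all. This is fair, and it is why the conflict is clearest in Tables 9 to 11. If the paragraph does not apply to Phase 1b, Tables 7 and 8 are left with the looser rule, apart from whatever the insert says. The protocol should therefore state whether it applies.

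A reader might also infer three stronger points that the documents do not support.

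- *That titration in the DLT window makes the cohort 3 and 4 MTD unusable.* Phase 2 titrates on the same day, so titrated axitinib is the relevant setting. The combination dose is set after review of toxicity and pharmacokinetics. An extra DLT from a wrongly raised dose would push the TRC105 dose down, which is the cautious direction. Every-two-week dosing in Phase 2 is optional and needs sponsor notification. The earlier titration to 7 and 10 mg without DLT (Section 2.3.4.1) does not settle the matter either way, because the cohort 1 and 2 windows closed before the scheduled increase.
- *That everyone with pressure above 150/90 is raised under the footnote.* This turns on CTCAE boundaries that are not in the documents.
- *That Table 5 is wrong, or that patients are on either 5 or 7 mg in the window.* Section 6.2.2 calls 5 mg the initial dose, and Section 6.2.6 allows reductions to 3 and 2 mg twice daily.

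**Conclusion.** The concern holds as a conflict between the footnote in five schedules and Section 6.2.6, and it is minor. It is shown for two kinds of patient: those with a continuing, clinically significant grade 2 reaction, and those on two antihypertensives for hypertension present and unchanged since entry. Each such patient raised to 7 mg receives 40% more axitinib per cycle than Section 6.2.6 intends. How many there would be is unknown. In Phase 2 the footnote wording is the same for both arms, so the text itself favours neither.

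The overlap with the DLT window in cohorts 3 and 4 is real. It supports applying the stricter criteria there, and nothing more.

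The conclusion assumes that some sites will act on the footnote as written, and that unchanged hypertension from before entry is not graded as an adverse reaction.

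**What to change.** Delete the dose-increase criterion from Table 7 footnote 12, Table 8 footnote 12, Table 9 footnote 11, Table 10 footnote 12 and Table 11 footnote 12. Put in its place either the Section 6.2.6 criteria or a plain reference to that section. Add one sentence to Section 6.2.6 stating that its titration rule also applies to Phase 1b.

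The cost is one sentence in each of five footnotes and one in Section 6.2.6. No new data are needed, since reasons for not raising the dose already go on the CRF.

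Two optional clarifications, which are not corrections:

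- Label the 5 mg in Table 5, and in its copies in the Synopsis and SAP Section 3.1, as the starting dose.
- Show the axitinib dose in force beside each DLT in SAP table 14.3.1.3, if the shell does not already do so. The doses are already in Listing 16.2.5.2.

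Axitinib should not be held at 5 mg through cycle 2, because that would depart from how Phase 2 doses. Patients within a cohort may then still be on different axitinib doses, as the protocol already allows.

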 15. **Baseline Emergent Adverse Events/Adverse Events:** Patients must be followed for safety from the day of informed consent until at least 28 days after the last dose of study treatment, or until all serious or axitinib related toxicities have resolved or are determined to be “chronic” or “stable”, whichever is later. Adverse events occurring prior to the initiation of the study treatment will be considered "Baseline-Emergent Adverse Events" and will be recorded on corresponding case report forms. Events that occur from the time the patient has taken the first dose of axitinib through 28 days after the last dose of axitinib will be recorded on “Adverse Event” CRFs. Any serious AE that is possibly related to axitinib occurring from the time of first dose or at any point after the reporting period must be promptly reported to TRACON.
 16. **Axitinib Pharmacokinetic Trough Concentration:** One 5 mL blood sample to be collected at the time-points indicated in the Schedule of Assessments, prior to dosing with axitinib. The morning dose of axitinib should be taken after the PK draw. Samples will be stored at approximately -70°C. Samples will be batch shipped as indicated in the laboratory manual to a third-party laboratory. See separate laboratory manual for further collection and shipment information. Additional PK samples may also be collected at the time of unexpected clinical events.
 17. **Protein Biomarkers:** One 10 mL purple top (K₂EDTA) tube will be collected at the time-points indicated in the schedule of assessments, prior to dosing with axitinib. The morning dose of axitinib should be taken after the Protein Biomarker draw. Samples will be stored at approximately -70°C to be analysed by a central laboratory. See separate laboratory manual for further collection and shipment information.
 18. **Archival Tumor Tissue:** Archival specimens (formalin-fixed, paraffin-embedded) are required of the primary cancer and/or metastatic cancer specimen for each study participant, if they are available. It is preferable that the entire paraffin block be submitted, but if this is not feasible, then at least 20 unstained slides are requested for immunohistochemical analysis (sections of 5 microns are preferred). Patients without available archival tumor tissue specimens are still eligible to participate in the study. See separate laboratory manual for further collection and shipment information.

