 19. **Cycle 3+ Treatment:** Patients who demonstrate a response of CR, PR or SD will be eligible for additional treatment until progression.
 20. **Follow-up:** The follow-up visit should occur 28 days following the last dose of axitinib. The allowable visit window is +/- 7 days.
 21. Allowable window for each visit within the cycle is +/- 2 days unless otherwise stated.

Table 10: Schedule of Assessments Phase 2: Arm B TRC105 + Axitinib (WEEKLY DOSING)

Protocol Activities	Screening	Cycle 1 and 2 [23]					Cycle 3+ [21] [23]				End of Study [3]	28 Day Follow-up [22]
	Day -28	Day 1 [1,2]	Day 4 (Cycle 1) [1]	Day 8 [1]	Day 15 [1]	Day 22 [1]	Day 1 [1]	Day 8 [1]	Day 15 [1]	Day 22 [1]		
Baseline Documentation												
Informed Consent [4]	X											
Medical/Oncology History [5]	X											
Physical Examination [6]	X	X					X				X	
Vital Signs [7]	X	X	X	X	X	X	X	X	X	X	X	
Laboratory Studies												
Hematology [8]	X + Fe	X + Fe (C1)			X		X		X		X	
Coagulation [8]	X	X										
Blood Chemistry [8]	X + TSH	X + TSH			X		X + TSH				X + TSH	
Pregnancy Test [9]	Day -7	X					X					X
Urinalysis [10]	X	X					X				X	
Treatment w/ Study Drug												
TRC105 [11]		X C1 Split	X C1 Split	X	X	X	X	X	X	X		
Axitinib Dosing [12]		Day 1				Day 28	Day 1				Day 28	
Tumor Assessments												
CT or MRI Scans [13]	X Including Brain	EVERY 56 DAYS FROM DATE OF RANDOMIZATION									X	
Bone Scans [13]	X											
Other Clinical Assessments												
12-Lead ECG [14]	X	X					X				X	
Concomitant Medications/Treatments [15]	X	X	X		X		X		X		X	X
Baseline-Emergent Adverse Events [16]	X											
Adverse Events [16]		X	X		X		X		X		X	X
Special Laboratory Assessments												
Pre-Dose PK [17]		X					Even Cycles				X	X
Anti-Product Antibody Testing (Arm B) [18]		X					Even Cycles				X	X
Protein Biomarkers [19]		X					Even Cycles				X	
Archival Tumor Tissue [20]	X											

Schedule of Assessments Footnotes Arm B (TRC105 + Axitinib):

1. **Days of Treatment with TRC105:** All assessments should be performed prior to the TRC105 infusion and axitinib dosing unless otherwise indicated. Each cycle is 28 days in duration.
2. **Cycle 1 day 1:** Hematology (including Fe studies), blood chemistry (including TSH testing), coagulation, urinalysis, physical examination, ECG and pregnancy test not required if acceptable screening assessment is performed within 7 days prior to the start of treatment on cycle 1 day 1.

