19. **Protein Biomarkers:** One 10 mL purple top (K₂EDTA) tube will be collected (pre-dose) at the time-points indicated in the schedule of assessments and stored at approximately -70°C to be analysed by a central laboratory. See separate laboratory manual for further collection and shipment information.

-
20. **Archival Tumor Tissue:** Archival specimens (formalin-fixed, paraffin-embedded) are required of the primary cancer and/or metastatic cancer specimen for each study participant, if they are available. It is preferable that the entire paraffin block be submitted, but if this is not feasible, then at least 20 unstained slides are requested for immunohistochemical analysis (sections of 5 microns are preferred). Patients without available archival tumor tissue specimens are still eligible to participate in the study. See separate laboratory guide for further collection and shipment information.
 21. **Cycle 3+ Treatment:** Patients who demonstrate a response of CR, PR or SD will be eligible for additional treatment until progression.
 22. **Follow-up:** The follow-up visit should occur 28 days following the last dose of TRC105 or axitinib whichever is later. The allowable visit window is +/- 7 days.
 23. Allowable window for each visit within the cycle is +/- 2 days unless otherwise stated.

Table 11: Schedule of Assessments Phase 2: Arm B TRC105 + Axitinib (EVERY TWO WEEK DOSING) *THIS SCHEDULE CANNOT BE FOLLOWED UNTIL NOTIFICATION FROM THE SPONSOR IS RECEIVED.**

Protocol Activities	Screening	Cycle 1 ^[23]					Cycle 2 ^[23]			Cycle 3 and Odd Cycles ONLY ^[21,23]		Cycle 4 and Even Cycles ONLY ^[21,23]			End of Study [3]	28 Day Follow-up [22]
	Day - 28	Day 1 ^[1,2]	Day 4 ^[1]	Day 8 ^[1]	Day 15 ^[1]	Day 22 ^[1]	Day 1 ^[1]	Day 15 ^[1]	Day 22 ^[1]	Day 1 ^[1]	Day 15 ^[1]	Day 1 ^[1]	Day 15 ^[1]	Day 22 ^[1]		
Baseline Documentation																
Informed Consent ^[4]	X															
Medical/Oncology History ^[5]	X															
Physical Examination ^[6]	X	X					X			X		X			X	
Vital Signs ^[7]	X	X	X	X	X	X	X	X		X	X	X	X		X	
Laboratory Studies																
Hematology ^[8]	X + Fe	X (C1)			X		X	X		X	X	X	X		X	
Coagulation ^[8]	X	X					X									
Blood Chemistry ^[8]	X + TSH	X + TSH			X		X + TSH	X		X + TSH		X + TSH			X + TSH	
Pregnancy Test ^[9]	Day -7	X					X			X		X				X
Urinalysis ^[10]	X	X					X			X		X			X	
Treatment w/ Study Drug																
TRC105 Dosing ^[11]		X C1 Split	X C1 Split	X	X	X	X	X		X	X	X	X			

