5.2. Patient Withdrawal Criteria

A patient should be withdrawn from study treatment if, in the opinion of the Investigator, it is medically necessary, or if it is the wish of the patient. If a patient does not return for a scheduled

visit, every effort should be made to contact the patient. In any circumstance, every effort should be made to document patient outcome. Data to be collected at the end of study visit are described in the Schedule of Assessments (Table 7, Table 8, Table 9, Table 10, and Table 11). Patients will be followed for at least 28 days after the last dose of TRC105 study drug for adverse events. If the patient withdraws consent, no further evaluations should be performed, and no attempts should be made to collect additional data. Patients may be withdrawn for DLT, but DLT does not mandate withdrawal if the DLT resolves and can be treated (i.e., a first dose infusion reaction).

Patients will be withdrawn from treatment in the case of:

1. RECIST 1.1-defined disease progression. In cases where RECIST cannot be applied, progression should be based on unequivocal evidence of progressive disease sufficient to require a change in therapy.
2. A need for anticancer surgery, radiation, or for other anticancer therapy not specified in the protocol.
3. Lost to follow-up or noncompliant.
4. Any TRC105 dose delay > 2 days in cycle 1 (phase 1b only cohorts -1, 1, and 2 only)
5. Pregnancy. Pregnant patients should be followed for the duration of the pregnancy and the outcome of the pregnancy should be documented.
6. Arterial thrombosis of any grade (including cerebrovascular ischemia, cardiac ischemia/infarction, or peripheral or visceral arterial ischemia), grade 3 or 4 venous thrombosis (including pulmonary embolism), grade ≥ 2 intracranial hemorrhage, grade 3 or 4 non-CNS hemorrhage. Grade 2 non-CNS hemorrhage does not mandate withdrawal if the underlying condition is treatable. Grade 1 intracranial hemorrhage does not mandate withdrawal and may be treated with dose interruption if the patient is benefitting from treatment.

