8.3. Reporting Adverse Events

8.3.1. Eliciting Adverse Event Information

The Investigator is to report all directly observed adverse events and all adverse events spontaneously reported by the trial patient using concise medical terminology. In addition, each trial patient will be questioned about adverse events at each clinic visit following initiation of treatment. The question asked will be, "Since your last clinic visit have you had any health problems?"

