8.3.2. Adverse Event Reporting Period

Safety information for each patient will be collected from the date of informed consent. Adverse events occurring prior to the initiation of the study treatment will be considered "baseline-emergent adverse events" and will be recorded on corresponding case report forms and will not be retained for patients who fail screening. The adverse event reporting period for this trial begins when the patient has taken the first dose of axitinib or TRC105 study drug and ends 28 days after the last dose of axitinib or TRC105 study drug is administered.

All adverse events that occur in trial patients during the adverse event reporting period specified in the protocol must be reported to TRACON, whether or not the event is considered study treatment-related. In addition, any known untoward event that occurs beyond the adverse event reporting period that the Investigator assesses as possibly related to the investigational medication/product should also be reported as an adverse event.

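### The 28-day follow-up visit may be held up to 7 days early, so the schedule does not assure adverse-event questioning to the end of the 28-day reporting period

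*Protocol*

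**What the plan says.** **Visit timing.** Table 9 (Arm A), footnote 20: "The follow-up visit should occur 28 days following the last dose of axitinib. The allowable visit window is +/- 7 days". Footnote 22 of Tables 10 and 11 (Arm B) starts the clock at the later of the two drugs, "The follow-up visit should occur 28 days following the last dose of TRC105 or axitinib whichever is later", with the same 7-day window either side. Footnote 22 of Tables 7 and 8 sets the same window for phase 1b, counted from the last TRC105 dose.

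**Length of safety follow-up.** Table 9, footnote 15: "Patients must be followed for safety from the day of informed consent until at least 28 days after the last dose of study treatment". The same footnote extends this for serious or related toxicities until they resolve or are judged chronic or stable, if that takes longer. It also defines what goes on the adverse-event form: "Events that occur from the time the patient has taken the first dose of axitinib through 28 days after the last dose of axitinib". Footnote 16 of Tables 10 and 11 is the counterpart for Arm B. Section 5.2 repeats the minimum: "Patients will be followed for at least 28 days after the last dose of TRC105 study drug for adverse events". Under Section 8.3.2 the reporting period "ends 28 days after the last dose of axitinib or TRC105 study drug is administered". SAP Section 12.2 ends the treatment-emergent period 28 days after the later last dose.

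**How events are collected.** Section 8.3.1 has investigators report what they observe and what patients volunteer, and adds active questioning: "each trial patient will be questioned about adverse events at each clinic visit following initiation of treatment".

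**Other items at this visit.** Footnote 9 of Tables 9 to 11 places a pregnancy test 28 days after the last dose. Those tables also show pharmacokinetic samples at the follow-up visit and, in Arm B, anti-product antibody samples.

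**The concern.** Twenty-eight days is a minimum for safety follow-up but the midpoint of the window for the visit that closes it. A site can keep to the schedule, see the patient for the last time on day 21, and have no further planned occasion to ask about the following week.

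The frequency and severity of adverse events is a named secondary objective (Section 3.1.2.2). The treatment-emergent tables treat every patient as observed to day 28. If some patients were last questioned a week earlier, the period actually covered by questioning is shorter than the period the tables imply, and its length varies with the date of the appointment.

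**Working it through.** The protocol states no figure to reproduce. The check is a day count, taking the last dose as day 0.

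**Inputs**
- Target visit day 28, window 7 days either side: Table 9 footnote 20; Tables 10 and 11 footnote 22.
- Required period 28 days: Table 9 footnote 15, Sections 5.2 and 8.3.2, SAP Section 12.2.
- End of Study visit generally within 7 days (+/- 1 day) of the last dose: footnote 3 of Tables 9 to 11.

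**Step 1: range of compliant visits**
- Earliest: 28 − 7 = day 21.
- Latest: 28 + 7 = day 35.
- Permitted days: 35 − 21 + 1 = 15.

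**Step 2: days left without scheduled questioning**
- A visit on day d leaves 28 − d days of the period after it.
- Worst case: 28 − 21 = 7 days (days 22 to 28), and 7/28 = 25% of the post-dose period.
- Visits on days 28 to 35 leave none.

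**Step 3: whether another contact fills the gap**
- The End of Study visit comes earlier, by about day 8.
- The follow-up visit is the last column of Tables 9, 10 and 11.
- Section 4.1.4 adds no telephone call or later visit.

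So when the follow-up visit is early, nothing is scheduled between it and day 28.

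**Step 4: how large the shortfall could be**

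The documents say nothing about where in the window visits will fall. The average loss lies between two limits: 0 days if every visit is on day 28 or later, and 7 days (25%) if every visit is on day 21. As an illustration only, assume visits spread evenly over the 15 days:
- Share of visits before day 28: 7/15 = 47%.
- Mean loss among those visits: (7 + 6 + 5 + 4 + 3 + 2 + 1)/7 = 4 days.
- Mean loss over all patients: 28/15 = 1.87 days, and 1.87/28 = 6.7% of the post-dose period.

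Visits clustered around day 28 would lose less than this.

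**Step 5: the same loss against the whole treatment-emergent period**

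That period also includes time on treatment. Assume treatment lasts about as long as the expected axitinib PFS of 4.8 months (Section 10.2.1), at 30.4 days per month:
- 4.8 × 30.4 + 28 ≈ 174 days.
- Even-spread case: 1.87/174 ≈ 1.1%.
- Every visit on day 21: 7/174 ≈ 4.0%.

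These are shares of time, not of events.

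**Step 6: effect of a 0 to +7 window**
- Visits fall on days 28 to 35, which is 35 − 28 + 1 = 8 permitted days.
- Days of the period left after the visit: 0.

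**The case against.** The strongest reply is that the 28-day duty does not depend on the visit. Footnote 15 of Table 9, Section 5.2 and Section 8.3.2 each state it in their own right, and the reporting period ends on day 28, not on the date of the visit. A site that stopped collecting at a day-21 visit would breach those rules, and the visit window would not excuse it. This stands. A reader might infer that the promised follow-up is simply not delivered, but the documents do not support that.

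A reader might also infer that unrelated events after an early visit are lost, because Section 4.1.4 asks only for related or possibly related events. That limit applies beyond the reporting period, so after day 28. For days 22 to 28, Section 8.3.2 requires every adverse event to be reported regardless of relatedness.

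There are other routes into the data. Observed and volunteered events are reportable (Section 8.3.1), and serious or possibly related events are followed after participation ends (Section 8.3.9). These narrow the gap but do not close it: volunteering is passive, and Section 8.3.9 concerns events already known. A new event that nobody mentions after an early visit has no scheduled way of being found. The opening of Section 8.3.3 was not in the text available for this check, so any contact rule there for serious events could not be read.

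The window is also the same in both phase 2 arms, so it gives no reason to expect bias between them. This too stands.

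**Conclusion.** The mismatch is real and minor. The protocol sets a 28-day minimum for adverse-event follow-up, but its visit schedule can leave up to 7 of those 28 days (25%) without planned questioning. The pregnancy test taken at the same visit may also fall before its stated time point. The exposure is confined to newly arising events that are neither observed nor volunteered between an early visit and day 28.

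Whether any rate is understated, and by how much, cannot be established from the documents. The 25% maximum follows from the protocol alone. The 47% and 6.7% figures rest on an assumed even spread of visits, and the 1.1% and 4.0% figures also rest on an assumed time on treatment. It would go too far to say that rates are understated, or that observation time differs by site, since the documents do not describe actual visit timing. The PFS analysis, sample size and error rates are unaffected.

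**What to change.** Either of two changes resolves it:

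1. **One-sided window.** In footnote 20 of Table 9 and footnote 22 of Tables 10 and 11, replace the window of 7 days either side with 0 to +7 days. Make the same edit in footnote 22 of Tables 7 and 8 for any phase 1b patients still to be followed. Section 2.3.4 reports that all eighteen planned weekly-cohort patients had been treated, so the Table 7 edit may matter little.
2. **Keep the window and add a contact.** State that after a visit before day 28, the site contacts the patient on day 28 to ask about adverse events. This covers adverse events but leaves the timing of the pregnancy test as it is.

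The first option adds no visit and brings both the final questioning and the pregnancy test to day 28 or later. It costs scheduling room (8 permitted days instead of 15), and a visit on days 21 to 27 becomes a deviation. Follow-up pharmacokinetic and anti-product antibody samples that would have been drawn early move slightly later. The second option costs one brief contact for each early visit.

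SAP Section 12.2 stays as it is under either option.
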